9.5.1. Specific safety measurements

Due to the short treatment duration, the topical administration (associated with a low risk of systemic availability of pyrethrum) and comprehensive data on the safety profile of the active substance, special safety investigations (e.g. laboratory safety tests) will not be performed. No further special safety investigations will be carried out during the study as sufficient information about the investigational products is already available.

9.5.2. Checks for general well-being

Checks for general well-being will be performed in a non-leading manner. In addition to the checks for general well-being at the first visit (0h, 1h p.a.), checks will also be performed, on study day 1 as well as on study day 7 (0h, 1h p.a.) and at the final visit on study day 10.

A registered physician will be available throughout the entire study and all subjects will be observed for signs of clinical toxicity during the entire study.

9.5.3. Pre-treatment signs and symptoms and Adverse Events

9.5.3.1. Definition of pre-treatment signs and symptoms and Adverse Events

An **Adverse Event (AE)** is any unintended or unfavorable sign (including an abnormal finding), symptom or disease occurring in a subject after signing the informed consent until the last study visit, whether or not the event is believed to be causally related to study medication (IMP) or comparative compound. This definition includes any worsening of conditions that were present at the time of entry into the study (signing of the informed consent) (see International Conference on Harmonization (ICH-E2A). AEs occurring after signing the informed consent but before administration of study medication are defined as non-treatment-emergent events. Those events are evaluated separately because in these cases a causal relationship with the study medication can be excluded.

Adverse Drug Reaction: In the pre-approval clinical experience with a new medicinal product or its new usages, particularly as the therapeutic dose(s) may not be established: all noxious and unintended responses to a medicinal product related to any dose should be considered Adverse Drug Reactions. The phrase "responses to a medicinal product" means that a causal relationship between a medicinal product and an Adverse Event is at least a reasonable possibility, i.e., the relationship cannot be ruled out. Regarding marketed medicinal products: a response to a drug which is noxious and unintended and which occurs at doses normally used in man for prophylaxis, diagnosis, or therapy of disease or for modification of physiological function (see the ICH Guideline for Clinical Safety Data Management: Definitions and Standards for Expedited Reporting).

Unexpected Adverse Drug Reaction: An Adverse Drug Reaction, the nature or severity of which is not consistent with the applicable product information e.g. Investigator's Brochure for an unapproved investigational product or package insert/summary of product characteristics for an unapproved product or package insert/summary of product characteristics for an approved product (see: ICH Guideline for Clinical Safety Data Management: Definitions and Standards for Expedited Reporting).

A Serious Adverse Event (SAE) / Serious Adverse Drug Reaction (Serious ADR) is defined as any untoward medical occurrence that at any dose results in death, or is life-threatening, or requires subject hospitalization or prolongation of existing hospitalization, or results in persistent or significant disability/incapacity, or results in a congenital anomaly/birth defect.

Important medical reactions that may not be immediately life-threatening or result in death or hospitalization but may jeopardize the subject or may require intervention to prevent one of the other outcomes listed in the definition above should also be considered serious.

Examples of such events are intensive treatment in an emergency unit or at home for allergic bronchospasm, blood dyscrasia or convulsions that do not result in hospitalization, or development of drug dependency or drug abuse.

The term "life threatening" in the definition refers to an event in which the subject was at risk of death at the time of the event; it does not refer to an event, which hypothetically might have caused death if it were more severe.

Hospital admission is usually interpreted as requiring at least one overnight stay. A requirement for out-subject treatment in an emergency room is not, by itself, an SAE although the event requiring treatment may be. Elective surgery or other elective procedures which require hospitalization are not SAEs if the condition being treated or investigated was preexisting at the time of entry into the study and did not worsen during the study. However, any untoward outcome of any such procedure should be reported as a non-serious AE or an SAE, as appropriate.

Persistent or significant disability or incapacity means that symptoms which disable the subject, defined as a substantial disruption in a person's ability to conduct normal life functions, do not resolve when study drug is discontinued. To ensure that there is no confusion or misunderstanding of the difference between the terms "serious" and "severe", which are not synonymous, the following should be considered: The term "severe" is often used to describe the intensity (severity) of a specific event (as in mild, moderate, or severe myocardial infarction); the event itself, however, may be of relatively minor medical significance (such as severe headache). This is not the same as "serious", which is based on subject / event outcome or action criteria usually associated with events that pose a threat to a subject's life or functioning. Seriousness (not severity) serves as a guide for defining regulatory reporting obligations.

Scientific and medical judgment should be used when deciding whether an event is serious. However, in situations where there is any uncertainty or ambiguity, the event should be managed and reported as if it were serious.

Suspected Unexpected Adverse Drug Reaction – SUSAR is an unexpected Serious Adverse Event causally at least possibly related to the investigational product. If a SAE will be classified as a SUSAR will be decided by sponsor's drug safety department.

9.5.3.2. AE-Assessment

Each AE will be assessed by an investigator according to the following categories:

Category	Characteristics	Explanations
Serious	Non-serious	
	Serious	
 • Results in death • Life threatening • Persistent or significant disability / incapacity • Hospitalization/Prolongation of existing hospitalization • Congenital anomaly/birth defect
Expected	Not applicable	
 • There is no causal relationship to investigational product assumed.
	No	
 • Nature, severity, intensity or outcome of the adverse reaction is not consistent with SPC/Investigator's Brochure.
	Yes	
 • Nature, severity, intensity or outcome of the adverse reaction is consistent with SPC/Investigator's Brochure.
Intensity	Mild	
 • Subject perceives signs or symptoms, but is easily able to tolerate those, his activity is not reduced.
	Moderate	
 • Signs and symptoms limit subject's normal activities, but don't stop them.
	Severe	
 • Subject is not able to pursue his normal activities.
Causal relationship to investigational product	No relation	Components of assessments of causal relationship 
 • Exposition: Was the investigational product really applied? • Time course: Was the administration of the investigational product followed by the AE in a reasonable time interval? • Probability: Are there other possible reasons for the AE, e.g. concomitant diseases, concomitant medication, environmental or individual factors? • Was the AE terminated or improved after reduction or the stop of medication? • Did the AE reoccur or worsen after reapplication of study drug?
	Possible relationship	
	Probable relationship	
	Certain relationship	
Action taken regarding study drug	None	
 • No change of the planned further application.
Category	Characteristics	Explanations
	Interrupted	
 • Application was interrupted for a short time.
	Disrupted	
 • Application was terminated.
Category	Characteristics	Explanations
	Increased	
 • Dose was increased.
	Reduced	
 • Dose was reduced.

	Unknown	
 • No details known.
	Not applicable	
 • Change of dose was not possible, because for instance application was terminated.
Outcome	Recovered/resolved	
 • The AE is completely subsided. There are no effects felt. Previous status is restored.
	Recovered with sequelae	
 • The AE is subsided, but subject suffers from symptoms, for instance persistent cough.
	Recovering	
 • The AE is improved, but subject still feels effects. Recovery is foreseeable.
	Ongoing	
 • The AE is not resolved, symptoms persist unchanged.
	Fatal	
 • Subject dies due to the AE.
	Follow-up impossible	
 • Outcome is unknown because subject didn't come to the follow-up visit. Efforts to get follow-up information failed.

9.5.3.3. Documentation and Reporting

Documentation of AE

Any AE, reported spontaneously by a volunteer or observed by the study personnel must be documented in the CRF regardless if causally related to the investigational product or not.

The following characteristics of an AE must be documented:

- Description of AE
- Time of onset and stop time
- Seriousness
- Expectedness
- Relationship to study drug
- Action taken regarding study drug
- Action taken regarding subject
- Outcome

Reporting of SAE (Serious Adverse Event)

All SAE causally related to study drug or not have to be documented using an additional SAE reporting form. The investigator must fax SAE report forms within 24 hours after receiving information about the occurrence of an SAE or changed information about a previously reported SAE to sponsor's drug safety.

Pharmacovigilance [name] Fax: [name]
--

If the SAE results in death, the investigator is obliged to provide further information on request of the ethics committee, the authorities or the sponsor. An event only classified as a SAE due to hospitalization starts at that time, when the subject arrives at hospital.

The initial SAE report should contain all available information at least:

- Study code
- Subject number
- Date of first dose
- Date of last dose
- Start time
- Description of SAE (diagnosis, symptoms)
- Individual subject data like age, gender
- Concomitant therapy
- Assessment of causality
- Name of investigator

Any effort must be made to get further information. If new information is received a follow-up SAE reporting form must be sent within 24 hours to the drug safety. The case report may be seen as complete if sufficient information regarding causal relationship and outcome is available and no further information is to be expected.

Follow-up of subjects after Adverse Events

The study staff of the clinical facility must monitor the trial subject's safety from the occurrence of an AE until recovery, return to baseline or a stable state will be achieved. In single cases follow up of an AE/SAE after last visit can be omitted if there is no causal relationship to study drug and subject's state is improved or stabilized.

Sponsor's responsibility

The sponsor should expedite the reporting to all concerned investigator(s) / institution(s) and to the regulatory authority(ies) of all AE's that are both serious and related. Such expedited reports should comply with the applicable regulatory requirement(s) and with the ICH Guideline for Clinical Safety Data Management: Definitions and Standards for Expedited Reporting.

9.6. Prior and concomitant therapy

Topical use of medication on scalp and hair, prior to the first intended administration of the investigational products, which is listed in the exclusion criteria (see section 8.6.1), will prevent inclusion into the study.

Treatment of a previous anti-lice treatment with exception of combing the hair using a lice comb within 30 days will prevent inclusion into the study. Treatment with an anti-lice treatment during the study will lead to exclusion of the subject.

Any pre-existing chronic medication taken for treatment of existing disorders and not considered to interfere with the study course or to influence scalp healing will be allowed.

Intake of pre-existing chronic medication used by the subject should be continued throughout the study at a conventional dose and schedule. Their use is to be recorded in the CRF and medical records.

Checks for concomitant medication will be performed at all study visits.

If a subject needs concomitant medication during the study, the responsible investigator should be asked. Concomitant medication is to be documented by brand, type (generic name, if applicable), amount and duration on the CRF. The Principal Investigator / investigator will then decide together with the responsible project manager of the study center, whether the subject must be excluded.

9.6.1. Concomitant treatment in the event of relevant AEs

Depending on the severity and type of the AEs, the following treatments are suggested treatments and may be changed at the discretion of the responsible physician.

Allergic reaction

Treatment with best standard treatment option according to the local investigator's site circumstances (e.g. antihistamines, glucocorticoids). The investigator will provide all the necessary emergency equipment at the study centre and specially trained staff to handle emergency events during this study (anaphylactic shock).

9.7. Appropriateness of measurements

All methods used for safety assessments are standard methods for which reliability, accuracy and relevance have been documented (e. g. pregnancy test).

9.7.1. Clinical laboratory parameters

In this study, no clinical laboratory parameters will be routinely determined.

9.7.2. Clinical parameters

Body weight and height will be measured with commercial instruments. Lice assessment will be done according to the instructions given in chapter 7.2. The study staff will be trained for combing and determine the live stages of lice.

9.8. Handling and documentation of clinical data

The Principal Investigator must ensure that all data required according to this protocol and not mentioned as exception in the following will be entered promptly in the CRF.

The following variables will be documented in the subject's records or in raw data sheets prior to transfer in the CRF. A paper CRF will be used in this study.

Category	Variables	Source	Details
Identification	Subject number, random number, screening number	Screening/enrolment log, subject file, random list	
Demographic data	Ethnic origin, gender, age, height, weight, participation in another clinical trial within 4 weeks,	Subject file or raw data sheet	
	Childbearing potential, pregnancy, breastfeeding, contraceptive method, result pregnancy test	Subject file or raw data sheet	Woman only

Description of study condition	Confirmation of head lice infestation, severity of head lice infestation, hair length, number of living head lice, live stage of lice	Subject file or raw data sheet	
Randomisation	Check inclusion/exclusion criteria	Subject file or raw data sheet	
	Randomisation	Enrolment log, Subject file	
	Reasons for non-inclusion into treatment	Subject file	
Concomitant medication	Trade name, indication, route, frequency, total daily dose, start date, stop date, ongoing	Subject file or raw data sheet	
Medical history	Disease, date of diagnosis, stop date, ongoing	Subject file or raw data sheet	Relevant findings
Safety	Local tolerability	Subject file or raw data sheet	
	Global tolerability by subject	Raw data sheet	
Category	Variables	Source	Details
	Global tolerability by investigator	Subject file or raw data sheet	prior to subject's assessment
	Skin irritation	Subject file or raw data sheet	
Category	Variables	Source	Details
	Eyes irritation	Raw data sheet	
	Satisfaction with the esthetical effect	Raw data sheet	
Administration	Amount of study medication, date of administration, start time, stop time	Drug dispensing log	
Completion	Date of completion, type of termination, reason for premature termination, date of premature termination, health state	Subject file	
AE	Description, start date/time, stop date/time, seriousness, severity, causal relationship, expectedness, action taken regarding study drug, action taken regarding subject	Subject file and raw data sheet	
PTSS	Description, start date/time, stop date/time, severity, action taken regarding subject, deterioration to AE	Subject file and raw data sheet	

In view of quality control, a member of the study team will check data on the CRF's for formal correctness, completeness and legibility of the entries.

Entries on the CRF's must be made with a ball-point pen and must be legible. Pencils and correction fluids are not to be used. If corrections are necessary, they will be entered by a member of the study team in

the following manner: the wrong CRF entry will be crossed out; however, it must remain legible, and the correct entry will be placed in the correction field (if applicable) or next to the wrong entry. Corrections will be initialed and dated.

A sample CRF is provided in the Trial Master File. The originals are to be returned to the Sponsor. One copy will remain at the Investigator's site. The CRFs for any subject leaving the study should be completed at the time when study participation is terminated. CRFs should accurately reflect data contained in subject's records (i.e. source documents).

9.9. Clinical data management

The data management department of the study centre will create a database, which reflects the final version of the CRF. Upon receipt of CRF's in data management, the information from the CRF's will be entered in the validated database according to the corresponding SOP's. Edit checks on completeness, correctness, plausibility (such as range checks, cross-checks) will be performed. All identified discrepancies will be queried by the data manager(s) using data discrepancy forms.

The completed data discrepancy forms will become part of the CRF and, therefore, the original data discrepancy form will be filed with the original CRF; copies must be archived at the centre. All changes to the database will be tracked (audit trail).

Details on data management procedures will be fixed in a detailed data management plan.

10. DATA ANALYSIS AND STATISTICAL CONSIDERATIONS

[name] (Adriaens Consulting, Bellem, Belgium) will perform all statistical analyses.

10.1. Sample size determination

Based on previous clinical data with comparable head lice products, a power analysis has been performed. Results indicated that a sample size of 30 subjects in both treatment groups result in a power of 80%.

10.2. Data Analysis Considerations

Based on previous clinical data with comparable head lice products, a power analysis has been performed. In order to detect superiority (superiority margin of 15%) of the test product (cure rate of 95%) over the reference product (cure rate 55%) with a power of 80% at 5% level of significance, 30 subjects are needed per treatment group.

10.3. Description

Continuous variables will be summarized by their mean, standard deviation (SD), median, minimum and maximum. Categorical data will be summarized by frequencies and percentages.

10.4. Efficacy Analyses

Efficacy analyses will be performed on the ITT population, consisting of all subjects who were included and randomized in the study, with available baseline value of the primary endpoint and at least one follow-up visit for the efficacy parameters. All statistical test will be performed at a 5% level of significance.

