6.5. Final evaluation visit (Day 10 + 2 days)

The final visit will be performed on study day 10 (+2 days). The final visit examination is performed to verify if the subject is cured. A subject will be considered cured, if no living head lice could be detected. If living lice present on day 10, the life stages of the lice will be documented. If any other pediculicidal agents was employed during the observation period, the subject will be considered a treatment failure (no efficacy analysis will be performed).

The following examinations will be performed within the final visit:

- Hair scalp assessment for living lice (all stages) by study staff (see chapter 9.4.8)
- Assessments of skin and eyes irritation, global tolerability, local tolerability
- Questioning on well-being
- Registration and documentation of any adverse events and/or changes regarding concomitant diseases, concomitant medication, withdrawal criteria
- Questionnaire on the satisfaction with the esthetical effect of the products
- Vital signs

In case that the examination (diagnostic combing) will show active head lice infestation (living nymph or imago), the subject will be considered treatment failure or re-infestation and will receive the standard of care at the site.

Subjects exhibiting either subjective or objective abnormalities when the trial has been completed will be followed up. Any AE which remains unresolved after completion of the trial requires detailed evaluation and follow-up until the AE has been resolved or a reasonable explanation for its persistence is found. If the subject refuses to follow the instructions of the study staff, the latter is released from responsibility.

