8.4.2. Follow-up of withdrawn subjects, drop outs

A drop out is a subject, who prematurely discontinues participation after being enrolled. If a subject drops out, possible AE's will be recorded as long as necessary. A post-study examination should be performed if possible.

All AE's documented during the study for the drop out will be considered in the assessment. Other data recorded for the drop out are contained in the individual subject listing in an appendix to the study report.

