8.5. Intention-to-treat (ITT) and Safety population

The safety set/population consists of all subjects who were randomised and exposed to study medication.

The ITT population contains any subject included and randomized in the study, with available baseline value of the primary endpoint and at least one follow-up visit for the efficacy parameters.

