10.4.1. Analysis of primary objective

The cure rate (p) corresponds to the proportion of subjects who are cured at day 10 among all subjects that received any treatment at day 0. The aim of the study is to show superiority for the cure rate of the test product versus a predefined limit of 70%.

The following null hypothesis will be tested:

$$H_{0, \text{prim}}: p_T - p_R = 0 \text{ and } H_a: p_T - p_R > 15\%$$

A χ^2 -test of independence will be used to test the null hypothesis.

In case superiority could not be proven, non-inferiority will be tested. According to ICH guideline “Points to consider on switching between superiority and non-inferiority” [17], it is allowed to assess non-inferiority in to the absence of superiority. Prerequisites include:

- predefinition of a non-inferiority margin
- no correction in terms of multiplicity

As non-inferiority margin (δ), a 7.5% worse cure rate is regarded as clinically not relevant. The following null hypothesis will be used: $H_{0, \text{NI}}: p_T - p_R < \delta$, whereby $\delta = -7.5\%$. The lower, 95% confidence interval (CI) of the difference $p_T - p_R$ will be used for the test. If $H_{0, \text{NI}}$ will be rejected, non-inferiority cannot be shown.

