19.1. Subject Withdrawal Procedures

If a subject is prematurely withdrawn from study participation for any reason, the Investigator must make every effort have the subject return to the clinic for a final evaluation. Subjects that withdraw early from

the study for any reason may be replaced with another subject to meet the original target of 50 subjects to complete the study.

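### The non-inferiority fallback is judged on the ITT set alone; if subjects lost or treated elsewhere are scored as not cured, it can pass somewhat too often

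*Combined protocol and SAP*

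**What the plan says.** Objective c in section 5.2 makes non-inferiority, with a 7.5% margin, a claim the trial may report when superiority is not shown. Section 10.4.1 carries it out: "In case superiority could not be proven, non-inferiority will be tested". The prerequisites listed there are a margin fixed in advance and no multiplicity correction; the analysis set is not mentioned.

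The set comes from section 10.4: "Efficacy analyses will be performed on the ITT population". The heading "8.5. Intention-to-treat (ITT) and Safety population" names the only two sets the plan defines. ITT means randomised subjects "with available baseline value of the primary endpoint and at least one follow-up visit for the efficacy parameters". There is no per-protocol set and no sensitivity analysis.

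The plan gives several answers on subjects who do not finish as planned:

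- Section 10.4.1 takes the cure rate "among all subjects that received any treatment at day 0", so anyone treated and not shown to be cured at Day 10 counts against the product.
- Section 8.5 drops subjects with no follow-up visit.
- Section 8.4.2, on drop-outs: "Other data recorded for the drop out are contained in the individual subject listing in an appendix to the study report".
- Section 6.5, on use of another pediculicide: "the subject will be considered a treatment failure (no efficacy analysis will be performed", which is both a failure and an omission. Section 8.4.1 makes such use a reason for withdrawal, and section 9.6 a reason for exclusion.

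**The concern.** In a superiority test, counting unassessed or off-protocol subjects as failures usually works against the claim, because it blurs a real difference. In a non-inferiority test the same blurring can help the claim. If some subjects in each arm are failed for reasons unrelated to the product, a product that is worse by the whole margin looks less than the whole margin worse. An analysis of subjects treated and assessed as planned would show whether the conclusion depends on this. The plan has none, so a non-inferiority statement would rest on one set whose contents are themselves not settled.

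**Working it through.** **Inputs from the plan.** Margin 7.5 points (5.2, 10.4.1); 35 per arm (8.1); 5% level, sidedness not stated (10.4); lower limit of a 95% interval, sidedness not stated (10.4.1). Both versions of the limit are therefore shown. Non-inferiority is taken as declared when the lower limit exceeds -7.5%.

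**Assumed.** Reference cure rate of 55% to 95% among subjects who complete as planned, and a share d of each arm failed regardless of product. The plan gives no drop-out rate; 0 to 30% is shown.

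**The plan's own figure.** The plan gives no error rate for the fallback, only a sample size for superiority. With cure rates of 95% and 55% and a 15-point margin:

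n = [0.95×0.05 + 0.55×0.45] × (1.645 + 0.842)² / (0.40 - 0.15)² = 29.2, so 30 per arm.

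This reproduces section 10.2 with a one-sided 5% level. A two-sided level needs 38. So the one-sided reading of the 95% limit cannot be set aside.

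**Dilution.** If the cure rates in completers are p_T = p_R - 0.075 and p_R, the expected ITT difference is (1 - d)p_T - (1 - d)p_R = -7.5 × (1 - d) points: -6.75 at d = 10%, -6.0 at 20%, -5.25 at 30%.

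**One case by hand** (p_R = 95%, d = 20%). The ITT rates are 0.875×0.8 = 0.70 and 0.95×0.8 = 0.76. SE = √[(0.70×0.30 + 0.76×0.24)/35] = 0.106. The chance of passing is Φ[(-0.060 + 0.075)/0.106 - 1.96] = Φ(-1.82), about 3.4%.

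**Exact rates.** All 36 × 36 outcomes were enumerated with the Miettinen-Nurminen score limit:

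| d in each arm | Two-sided 95% limit, p_R = 95% | Two-sided, p_R 55-95% | One-sided 95% limit, p_R = 95% | One-sided, p_R 55-95% |
|---|---|---|---|---|
| 0% | 2.3% | 2.3-2.6% | 4.7% | 4.4-5.2% |
| 10% | 2.8% | 2.8-3.0% | 5.6% | 5.1-6.0% |
| 20% | 3.5% | 3.3-3.5% | 6.8% | 5.8-6.8% |
| 30% | 3.8% | 3.8-3.9% | 7.4% | 6.5-7.4% |

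Newcombe limits give the same two-sided ranges at 10% and 20%.

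**Unequal loss** (normal approximation, two-sided 95% limit):

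| Loss, test / reference | p_R | Expected ITT difference | Chance of passing |
|---|---|---|---|
| 5% / 15% | 55% | -1.6 points | 7.1% |
| 5% / 15% | 95% | +2.4 points | 18.8% |
| 15% / 5% | 55% | -11.9 points | 1.0% |
| 15% / 5% | 95% | -15.9 points | 0.2% |

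For example, with p_R = 55% and 5% / 15% loss: 0.475×0.95 - 0.55×0.85 = 0.451 - 0.468 = -0.016.

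**If these subjects are left out**, and loss is unrelated to outcome, the expected difference stays at -7.5 points and there is no dilution.

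**With a per-protocol analysis**, on the same assumption, about 32 per arm remain at d = 10% (35×0.9) and 28 at d = 20% (35×0.8). Exact Newcombe error rates for the per-protocol analysis alone are 1.5-2.7% and 1.5-2.9%. Requiring both sets to pass cannot exceed these.

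**The case against.** The strongest reply is that the dilution is not a documented feature of the plan. It needs these subjects to be kept and scored as failures. The denominator in 10.4.1 and the failure label in 6.5 point that way; the omission clause in 6.5, the listing in 8.4.2 and the exclusion in 9.6 point the other way. This stands, and it is why the point is conditional. It also shows that adding a per-protocol set is not enough, because the ITT half of the comparison would remain undefined.

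The effect under equal loss is also small: 0.3 to 1.0 points above the nominal 2.5% at 10-20% loss. Follow-up ends at Day 10 to 12 and staff apply the product on site, so departures may be few. With truly equal products, the exact chance of showing non-inferiority at 35 per arm is only about 9-22% (two-sided limit), so the fallback will seldom succeed. All of this supports treating the matter as an inexpensive improvement.

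Three stronger readings are tempting and are not supported:

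- A reader might infer about 29% loss from 50 completers out of 70 enrolled. Section 19.1 says withdrawn subjects may be replaced "to meet the original target of 50 subjects to complete the study". That is a completion target under replacement, in conflict with the no-replacement rule in 8.1 and 8.4.4. It is not an attrition estimate.
- A reader might count a missed second application as an automatic failure. No section scores it so; Day 10 status depends on whether live lice are found.
- A reader might conclude that ITT always favours non-inferiority here. The unequal-loss figures show it can work either way.

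Finally, a per-protocol set is not free of bias. Severe irritation before the second application, or use of another pediculicide, may be consequences of the assigned product.

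**Conclusion.** The gap is real: a claim the trial may report rests on the ITT set alone, with no per-protocol check. If non-completers and users of other pediculicides are scored as not cured, and 10-20% of each arm is lost at random, the chance of a false non-inferiority claim at a true -7.5 points rises from about 2.5% to 2.8-3.5% (two-sided 95% limit) or from about 5% to 5.1-6.8% (one-sided). These figures assume 35 per arm and a reference cure rate of 55-95%; the loss shares are assumptions.

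Size and direction are conditional. Heavier loss in the reference arm is the more serious case (7.1% to 18.8% at 5% / 15%). It cannot be ruled out, because section 8.3 says subjects and applying staff will recognise the products. Heavier loss in the test arm lowers the rate, and omission removes the dilution. The plan does not settle which handling applies, and that should be decided before the data are seen. This is a correctable weakness in a secondary claim and leaves the superiority analysis untouched.

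**What to change.** 1. In 8.5, define a per-protocol set from criteria the protocol already contains: both applications given with the stated contact times, no other pediculicide, Day 10 assessment within its visit window, and no major eligibility violation. In 10.4.1, declare non-inferiority only if the lower limit exceeds -7.5% in both the ITT and the per-protocol set. Keep superiority on ITT.
2. Reconcile 6.5, 8.4.1, 8.4.2, 8.5, 9.6 and 10.4.1 into one rule on whether non-completers and users of another pediculicide count as failures or are left out of the ITT analysis.

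**Cost.** A few sentences and one more run of the same analysis. Application times, concomitant medication, lice counts and completion are already to be recorded (7.3, 9.8), so no new data are needed. Non-inferiority becomes slightly harder to claim. The per-protocol set is smaller and can be biased if exclusions relate to outcome, so the reasons for exclusion should be tabulated by arm.
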